Cost-analysis on R-SS compared to laparoscopic multiport hysterectomy in benign gynecology has a knowledge gap. A retrospective study suggests increased cost per case using R-SS compared to laparoscopic multiport hysterectomy (7)(El Hachem et al. 2016). A variety of circumstances influences the analyses such as already established infrastructure for robotic surgery at the hospital, high volume versus low volume robotic centers and experienced robotic teams. Cost-effectiveness analyses are essential in order to provide a responsible utilization of health care resources and includes determination on sick-leave, consultation to healthcare (ex kontakt I amb ell e.l. pga kir.relatedede problemstilling). If out-of-hospital costs are included these may vary between countries; however, the phase between hospital stay and return to work may imply extra cost for the patient, need for reimbursement from health insurances, visits to medical professionals due to related morbidity a.s.o. If rehabilitation with RSS is shorter and includes less extra medical cost and visits the total cost may be less.

Summary:

R-SS hysterectomy is a novel technique, which may be superior to conventional laparoscopic multiport hysterectomy in select patients regarding sick-leave, cosmesis and postoperative pain. We, therefore, aimed at evaluating the learning curve using different robotic equipment (DaVinci Si Multiport surgical system and DaVinci Xi multiport and single site surgical system) in our cohort since 2014 to determine its applicability in our hospital setting. Secondly, we perform a randomized trial to compare R-SS hysterectomy with conventional laparoscopic multiport hysterectomy with regard to outcome postoperative rehabilitation, cosmesis, and the operational cost

Aim of study

Our study aims to evaluate R-SS with respect to:

Primary outcome:

- Length of hospital stay and time to return to daily activities /work
- Cosmesis; pre-and postoperative evaluation
- Postoperative pain (VAS)

Secondary outcome

- Learning curve for robotic-assisted hysterectomy including R-SS hysterectomy
- Patient satisfaction with the cosmesis
- Duration of operation incl. detailed information of time consumption of defined steps at hysterectomy, operation- and console time, blood loss, conversion rates, additional ports, port-site hernias, time at hospital, re-admission
- Cost-effectiveness analysis for the R-SS hysterectomy

Materials and Methods

Study 1:

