The study is scheduled to start May 2018 and compares R-SS hysterectomy to laparoscopic multiport hysterectomy. Procedures are performed by an experienced three-surgeon team. Patients are randomized to either laparoscopic multiport hysterectomy (N=62) or R-SS hysterectomy (N=62) by random numbers in sealed envelopes prepared by a third party. Eligibility criteria are the same as for study 2B (i.e. BMI < 30 kg/m²). Patient's satisfaction with body image and cosmesis is assessed at different time points pre- and postoperatively by means of multidimensional body-self relations questionnaire – appearance evaluation sub-scale and POSAS. Postoperative pain and analgesia use will

be registered as well as secondary outcome parameters as described above. A follow-up at one, three, and six month include self evaluation of the scar and registration of port-site hernias, vaginal dehiscence or other complications (Vercellia et al). Interviews and diaries will include time of return to home and work, daily activities including sexuality

The R-SS hysterectomy is performed using da Vinci, Xi robotic system. One single port, diameter 2 cm is applied at the umbilicus. Applying an additional assistant port is defined as conversion of procedure

The laparoscopic multiport hysterectomy is performed using our standard equipment and 4 trocars, 5 mm each.

Study 3

Socio-economical consequences of R-SS hysterectomy versus conventional laparoscopic hysterectomy

Study details in preparation

Instrumental cost

Hospital stay

Post-hospitalization cost. sick days, extra visits to the out-patient clinic, general practitioner, medical expenses

Sample size calculation was based a PhD- study on fast track hysterectomy, which showed a difference in return to work of 4 days and SD ± 8 . 62 women in each group are needed for a power of 80% (beta=0.2) to replicate this study. To include those not working, we calculated that with an expected VAS of 0.86 ± 0.2 and 62 in each group the sample was sufficient to detect a difference of 0.1 in VAS; still, with a power of 80%. All calculations are based on two-sided testing with alpha = 0.05.

The retrospective study was approved by the Data Authority (no. 1-16-02-913-17). The randomized trial is registered at clinicaltrials.gov (NHS).

Statistics

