For statistical calculations of proportions the χ^2 -test with Yates' correction for discontinuity or the Fisher's Exact-test was used. For continuous variables Student's t-test, Mann-Whitney's U -test, and Wilcoxon's Signed Rank test was used when appropriate.

Questionnaires with partial answers were included in the calculations, if possible. ANOVA and Kruskal Wallis' test was performed between group variables. Post-hoc test with Newman-Keul's test was performed between group pairs, if ANOVA was significant.

Repeated measurements were evaluated with 2-way ANOVA and surgical procedure as group variable with potential confounding variables like age, BMI, surgeon, and additional surgery added. The distribution of BMI, age, blood loss, split times during operation, hospital stay and time of return to daily activities and work were evaluated by means of Kaplan-Meyer analysis. The level of significance was a two-sided $p < 0.05$. Logistics regression analysis was performed with surgical procedure as dependent variable and the various split times, surgeon, age, BMI, parity, as independent variables. Learning curves were established for each individual surgeon, surgical procedures, and combined

monitored over time of the studies. Data are given as mean \pm SD if following Gaussian distribution and median (minimum, maximum) if non-Gaussian distributed. IBM SPSS Statistics 20 was used as the statistical software

Research plan

Study 1; jan 2017-june 2018

Study 2; may. 2018-jan. 2020

Study 3; 2020-2021

Responsibility:

[name] [name], [name]. Department of Gynecology and Obstetrics, Herning Hospital, Principal data supervisor and investigator for clinicaltrials.gov
[name], Ph.D. Department of Gynecology and Obstetrics, Herning Hospital

References

El Hachem, L., et al. (2016). "Robotic Single-Site and Conventional Laparoscopic Surgery in Gynecology: Clinical Outcomes and Cost Analysis of a Matched Case-Control Study." *J Minim Invasive Gynecol* **23**(5): 760-768.

Golkar, F. C., et al. (2012). "Patients' perceptions of laparoendoscopic single-site surgery: the cosmetic effect." *Am J Surg* **204**(5): 751-761.

Sandberg, E. M., et al. (2017). "Laparoendoscopic single-site surgery versus conventional laparoscopy for hysterectomy: a systematic review and meta-analysis." *Arch Gynecol Obstet* **295**(5): 1089-1103.

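### The planned 2-way ANOVA for repeated measurements does not name the preoperative body-image score as a covariate; adjusting for it would gain power at almost no cost if it correlates clearly with later scores and the effect is steady

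*Protocol*

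**What the plan says.** Under Aim of study, the primary outcomes include "Cosmesis; pre-and postoperative evaluation". Study 2 says that satisfaction with body image and cosmesis is "assessed at different time points pre- and postoperatively by means of multidimensional body-self relations questionnaire" (its appearance evaluation sub-scale) and by POSAS. Follow-up is at one, three and six months.

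The Statistics section states: "Repeated measurements were evaluated with 2-way ANOVA and surgical procedure as group variable", "with potential confounding variables like age, BMI, surgeon, and additional surgery added". On incomplete forms it says: "Questionnaires with partial answers were included in the calculations, if possible".

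The sample-size paragraph covers two other outcomes. For return to work (difference 4 days, SD 8) it says "62 women in each group are needed for a power of 80% (beta=0.2) to replicate this study". For pain (SD 0.2) it says "the sample was sufficient to detect a difference of 0.1 in VAS". It gives no SD, target difference or pre-post correlation for body image.

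**The concern.** A woman's preoperative score on the same scale is usually the natural covariate for her later scores. The protocol names four other covariates and leaves this one unmentioned. The word 'like' keeps the list open, so the score is not excluded, but its role is not settled.

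The role matters because the same data support tests of very different power. If the preoperative score is a level of the time factor, the procedure main effect averages in a visit at which no effect of surgery can exist, which dilutes the difference. The procedure-by-time test avoids that dilution. However, with one postoperative visit it is the change-score comparison, and with several visits it spreads a steady effect over several degrees of freedom. If the preoperative score is left out, its information is lost. If it is a covariate, the arm difference is estimated more precisely with the same 124 women.

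**Working it through.** **The plan's own figure.** Both sized outcomes have the same standardised effect: 4/8 = 0.5 and 0.1/0.2 = 0.5. With two-sided alpha 0.05 and 80% power, n per arm = 2(1.960 + 0.842)²/0.5² = 62.8, so 63 against the stated 62. At 62 per arm the exact t-test has 78.9% power. The stated size is reproduced, and nothing below changes it.

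**Inputs.**
- From the protocol: 62 per arm, two-sided alpha 0.05, and 0.5 SD as the effect size used for the other outcomes.
- Assumed: correlation rho, number k of postoperative body-image visits, equal correlation between all visits, unit SD, and the effect on body image.

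**Formulas.** The standard error is sqrt(2V/62), and power comes from the noncentral t with 122 df (121 when adjusted).
- Postoperative mean only: Vp = (1 + (k − 1)rho)/k
- Adjusted for the preoperative score: V = (Vp − rho²)(1 + 1/120), where the last factor allows for chance covariate imbalance with N = 124
- Change from the preoperative score: V = Vp + 1 − 2rho
- Main effect with the preoperative score as a level: V = (1 + k·rho)/(k + 1), with the effect shrunk to k/(k + 1) of the mean postoperative effect
- Procedure-by-time: noncentral F with k and 122k df, lambda = 31·SS/(1 − rho), where SS is the sum of squared deviations of (0, effects) from their mean

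**Worked case, k = 1, rho = 0.5, effect 0.5 SD.**
- Adjusted: V = 0.75 × 1.00833 = 0.756, SE = 0.156, noncentrality 0.5/0.156 = 3.20, power 88.8%.
- Postoperative only: V = 1, SE = 0.180, noncentrality 2.78, power 78.9%.
- Main effect including the preoperative visit: V = 0.75, effect 0.25, SE = 0.156, noncentrality 1.61, power 35.8%.

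**One postoperative visit, 0.5 SD (power, %).**

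| rho | 0 | 0.1 | 0.3 | 0.5 | 0.7 |
|---|---|---|---|---|---|
| Adjusted | 78.5 | 78.9 | 82.2 | 88.8 | 97.1 |
| Postoperative only | 78.9 | 78.9 | 78.9 | 78.9 | 78.9 |
| Change, or procedure-by-time | 49.7 | 53.9 | 64.6 | 78.9 | 94.6 |
| Main effect including preoperative | 49.7 | 46.1 | 40.3 | 35.8 | 32.2 |

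At rho 0.3/0.5/0.7 adjustment cuts the variance by rho² = 9/25/49% against postoperative only. That is worth 124/(1 − rho²) = 136/165/243 women instead of 124.

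**Three postoperative visits, steady effect (power, %, at rho 0.3/0.5/0.7).**

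| | 0.3 SD | 0.5 SD |
|---|---|---|
| Adjusted | 69.8/72.5/84.2 | 98.5/98.9/99.9 |
| Postoperative only | 62.1/52.8/45.7 | 96.6/92.3/87.0 |
| Change | 40.4/52.8/74.5 | 81.6/92.3/99.2 |
| Procedure-by-time | 27.1/37.0/58.3 | 66.7/82.3/96.9 |
| Main effect including preoperative | 43.8/34.9/29.2 | 85.2/74.5/65.3 |

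**Fading effect, 0.5/0.25/0 SD at three visits (power, %, same rho).** Procedure-by-time 62.5/78.5/95.5; adjusted average 54.2/56.8/69.5; adjusted contrast at a first visit named in advance 82.2/88.8/97.1. A named visit with no effect rejects in about 5%.

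**Check.** Simulation with 10,000 runs per one-visit scenario gave, for the adjusted analysis at rho 0/0.1/0.3/0.5/0.7, 79.0/78.9/82.3/89.4/96.6%. With no effect, all four analyses rejected in 4.6 to 5.6% of runs.

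**The case against.** The strongest reply is that the protocol makes no mistake here. The covariate list is open, an analysis plan not shown may name the preoperative score, and the unadjusted randomised comparison is valid. That stands, and it is why this is a suggestion. The Statistics section does, however, commit to a model and name covariates, and as worded it allows readings that differ widely in power.

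Two links are inferred. The ANOVA sentence names no outcome; body image is a natural reading because it is measured repeatedly, before and after surgery. Its primary status is also not beyond doubt: Aim of study lists cosmesis as primary but patient satisfaction with the cosmesis as secondary, and Study 2 introduces the questionnaire in terms of satisfaction. The pre- and postoperative wording favours the primary reading.

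The size of the gain rests on assumptions. The one-, three- and six-month visits are described for scar self-evaluation and complications, not expressly for the body-image questionnaire. At a steady 0.5 SD over three visits, the gain over postoperative scores alone is about 2/7/13 points at rho 0.3/0.5/0.7, against about 8/20/38 points at 0.3 SD.

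Last, nothing in the protocol shows that the effect is steady. If it fades as assumed above, the adjusted average loses about 8/22/26 points to procedure-by-time. A named visit recovers this only if the right visit is chosen. This objection stands in full: the low cost applies to the covariate itself, not to a poorly chosen contrast.

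**Conclusion.** The point holds as an optional improvement. The preoperative body-image score is collected, but the protocol does not name it as a covariate or settle its role. With rho of 0.3 or more and a steady effect, adjustment had the highest power of every reading examined. With one visit at 0.5 SD it gains about 3/10/18 points over postoperative scores alone at rho 0.3/0.5/0.7, and more over a main effect that includes the preoperative visit.

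There is no useful gain over postoperative scores alone at rho 0 to 0.1 with one visit, and none if the open list already includes the score as a covariate. These figures rest on the assumed correlation, effect, number of visits and equal correlation between visits. Validity is not in question, and the 62 per arm does not change.

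**What to change.** For body image in the randomised comparison, analyse the postoperative scores with a repeated-measures or mixed model. Include procedure, visit, procedure-by-visit and surgeon, with the preoperative score as a covariate and not as a level of the outcome. State in advance which procedure contrast tests the arms: the average over postoperative visits, or one named visit if the effect is expected to fade. Add a simple rule for missing preoperative scores, such as mean imputation, so that no randomised woman is dropped for that reason. Analyse POSAS on postoperative visits without a preoperative covariate, because the surgical scar has no preoperative score. If the open list was already meant to include the preoperative score as a covariate, one sentence saying so settles that part.

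The cost is wording in the Statistics section, the missing-score rule and one degree of freedom, worth 0.4 points of power at rho = 0 (78.9% to 78.5%). No extra women or visits are needed.

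### The 2-way ANOVA for repeated scores either excludes women with a missed visit or ignores within-woman correlation, depending on how it is run; a mixed model on all available visits avoids both

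*Protocol*

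**What the plan says.** The Statistics section of the Protocol fixes the method: "Repeated measurements were evaluated with 2-way ANOVA and surgical procedure as group variable with potential confounding variables like age, BMI, surgeon". Additional surgery is also listed as a covariate. On software it says only: "IBM SPSS Statistics 20 was used as the statistical software". It does not say which SPSS procedure is meant, or which outcomes count as repeated measurements.

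The outcomes can be inferred from elsewhere. The primary outcomes under Aim of study include "Cosmesis; pre-and postoperative evaluation". Study 2 says: "Patient's satisfaction with body image and cosmesis is assessed at different time points pre- and postoperatively". It adds: "A follow-up at one, three, and six month include self evaluation of the scar". These are the clearest serial patient-reported scores in the randomised trial.

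The one sentence on incomplete data, also under Statistics, is: "Questionnaires with partial answers were included in the calculations, if possible". Nothing is said about a visit with no form or a woman who leaves follow-up. The sample-size paragraph states 62 women per arm as the number needed. Study 2 randomises 62 per arm, so there is no allowance for losses.

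**The concern.** A 2-way ANOVA of repeated scores has two ordinary readings, and each has a defect.

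- **Classical repeated-measures ANOVA, one row per woman.** A value is needed at every time point, so a woman who misses one form leaves this analysis along with the scores she did give.
- **Two-factor ANOVA (procedure by time) on stacked visits.** She stays in, but several scores from one woman count as independent observations.

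Under the first reading the comparison on a primary outcome loses women. It can also be biased if the reasons for missing a form relate to the scores differently in the two arms. That is conceivable, because a woman can see whether she has one incision or four. Under the second reading the standard errors, and hence the p-values, are wrong even with no missing data. The first reading also works against the plan's own wish to use partial questionnaires.

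**Working it through.** **Inputs.** From the Protocol: 62 women per arm; follow-up at one, three and six months, plus a preoperative body-image assessment; two-sided alpha 0.05; and, for the sample size, a study that "showed a difference in return to work of 4 days and SD ± 8". The Protocol gives no rate of missed forms and no within-woman correlation, so both are assumed below.

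**1. The plan's own figure.** The standardised difference is 4/8 = 0.5. Per arm, n = 2 × (1.96 + 0.842)² / 0.5² ≈ 62.8, so 63. At 62 per arm, power = Φ(0.5 × √(62/2) − 1.96) = Φ(0.824) = 0.795. The stated 62 for 80% power reproduces within rounding. It was derived for return to work and VAS pain, not for cosmesis, and serves here only as a yardstick.

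**2. Reading one: women left after exclusion.** If a fraction p of forms is missed independently at each of k time points, complete cases = 62 × (1 − p)^k. Power is for one comparison at 0.5 SD.

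| Assumed p | k = 3 (postoperative visits) | Power | k = 4 (with preoperative) | Power | Women with a 6-month score, 62 × (1 − p) |
|---|---|---|---|---|---|
| 5% | 53.2 | 0.73 | 50.5 | 0.71 | 58.9 |
| 10% | 45.2 | 0.66 | 40.7 | 0.62 | 55.8 |

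Independence matters. If the losses are withdrawals only, 10% in total leaves 62 × 0.9 = 55.8 per arm (power 0.75) and 20% leaves 49.6 (power 0.70).

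**3. Reading one: bias.** A simulation used 200,000 women per arm, four time points, correlation 0.6 and no true arm difference. Women dropped out after month 1 with logit probability −2 + slope × month-1 score. The estimand was the arm difference in the mean of the three postoperative visits.

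| Dropout and score | Dropout by arm | Complete cases (SD) | Likelihood-type estimate (SD) |
|---|---|---|---|
| Unrelated | 12% / 12% | 0.003 | 0.003 |
| Related equally in both arms | 16% / 16% | 0.003 | 0.003 |
| Related in one arm only | 12% / 16% | −0.098 | 0.003 |
| Related in opposite directions | 16% / 16% | −0.200 | 0.004 |

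A second simulation (400 trials, 62 per arm) had 15% random dropout in one arm and about 20% in the other, higher after a poor 1-month score. The mean 6-month difference was 0.149 SD from complete cases and 0.009 SD from a mixed model. The standard error in a single trial was about 0.19 SD for both methods.

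**4. Reading two: wrong standard errors.** Take k visits with common correlation ρ. The true variance of the arm difference averaged over visits is 1 + (k − 1)ρ times the variance that stacking assumes. With ρ = 0.6 this is 2.2 for k = 3 and 2.8 for k = 4. The actual size of a nominal 5% test is 2 × [1 − Φ(1.96/√2.2)] = 0.19 and 2 × [1 − Φ(1.96/√2.8)] = 0.24. A simulation at 62 per arm with no missing data gave about 18.5% and 24%.

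**The case against.** A reader might infer that the plan drops every woman who misses one visit and discards all her data. The Protocol does not support that. It names no SPSS procedure and never says such women are excluded. Exclusion is a property of classical repeated-measures ANOVA, known from general statistical practice. Under the stacked reading she is kept. Even under the first reading, her data leave that one analysis only. The Statistics section also lists t, Mann-Whitney and Wilcoxon tests, which can use the scores available at a visit, and Kaplan-Meier analysis for hospital stay and return to activities. Nor does it designate the repeated-measures ANOVA as the main test for cosmesis. All of this stands and limits the claim.

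A reader might also infer that the trial will be biased. That does not follow. Attrition is undocumented, and the bias needs a mechanism that differs by arm. The 0.149 SD found in one scenario is smaller than the standard error of a single trial, and the mixed model showed no gain in precision there. The simulated dropout also depended only on the observed 1-month score, which is the condition under which a mixed model works. Dropout driven by later, unobserved scores would bias both methods.

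Finally, model details and the handling of missed visits often sit in a statistical analysis plan, and none is shown here. That would excuse silence. It does not excuse a named method whose ordinary readings are both flawed. The partial-answers sentence does lean towards keeping data, but it speaks of questionnaires that came back. It gives no rule for one that did not.

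**Conclusion.** The point holds in conditional form. The Protocol fixes a 2-way ANOVA for repeated measurements, and applying it to the Study 2 cosmesis and scar scores is an inference, though a sound one.

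If it is run as classical repeated-measures ANOVA, about 45 to 53 of 62 women per arm remain with 5% to 10% of forms missed independently at each of three visits. The arm comparison is then off by about 0.1 to 0.2 SD in the scenarios where missingness relates to scores differently by arm, and by almost nothing otherwise. If it is run on stacked visits, no woman is lost, but the test of the overall arm difference has a true size near 19% to 24% at an assumed correlation of 0.6. The missing-form rates, the dropout mechanisms and the correlation are all assumptions.

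This is a weakness in a stated method that is cheap to repair. It is not evidence that the trial's result will be wrong.

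**What to change.** In the Statistics section, replace the 2-way ANOVA for the repeated Study 2 scores with a linear mixed model (MIXED in SPSS):

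- fixed effects for visit, randomised arm and arm-by-visit;
- the covariates already planned (age, BMI, surgeon, additional surgery);
- a within-woman covariance;
- all available visits of every randomised woman, including those who miss visits or withdraw.

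Report the arm contrast at each visit and name in advance which one is primary. The Protocol designates no time point for cosmesis, so this is a choice for the trial team and should be stated as one. Say also that the partial-answers sentence concerns returned forms with blank items, and that absent forms are handled by the model.

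The cost is a little more analysis work, with no new data and no new software. The model assumes that missingness is explained by observed data. That is weaker than what a complete-case analysis needs, but it does not protect against dropout driven by unobserved later scores, and the text should say so.

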Robotic-assisted benign hysterectomy – learning curve for surgeons and a randomized comparison of robotic single-site hysterectomy vs. multi-port laparoscopic hysterectomy

Background:

Robotic-assisted surgery in gynecology is one of the fastest growing fields of robotic surgery. In Denmark yearly 4000 hysterectomies are performed on benign indications (1) and minimal invasive technique used in hysterectomies has increased from 35 % to 80 %. These include vaginal, laparoscopic assisted and lately robotic-assisted hysterectomy. The robotic surgical system Da Vinci was introduced in 2000. By 2016, 3803 units were established worldwide and 644 of them in Europe. Hysterectomy and prostatectomy is by far the most common operations performed with the Da Vinci robot. Robotic-assisted surgery is an alternative to conventional laparoscopy allowing better ergonomy for the surgeon and precise movements due to endo-wristed instruments.

Robotic surgery in benign gynecology is still a matter of debate, due to expensive costs and lack of evidence of superiority to conventional laparoscopy regarding perisurgical outcome.

A new approach in hysterectomy is the robotic single-site technique (R-SS), which is based on one single incision compared to standard four incisions in multiport robotic- as well as conventional laparoscopy. This wound-sparring technique may reduce postoperative pain, allowing shorter hospitalization, shorter sick leave and better cosmesis. Since fast-track regimes are gaining ground in gynecology there is a need for detailed information about the new surgical technique, especially whether it can replace conventional multiport laparoscopy.

Determination of learning curves for a novel surgical technique like the robot provides valuable information regarding safety as well as applicability. For these reasons proper knowledge is important to which extent e.g. BMI, uterine size, and docking time at the robotic console influence the procedure. Secondly, the proper patient selection could be established for the various surgical options. To date, there are no detailed reports on robotic single-site hysterectomy using the newest robotic technology, the da Vinci, Xi system.

Multi-port versus Single-site in laparoscopic surgery

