Detailed learning curves for robotic surgery- single site and multiport hysterectomy – a prospective, controlled study. A retrospective study of all robotic hysterectomy since 2014

The prospective controlled study compares R-SSH with robotic multiport hysterectomy (the controls) and will be performed at the Department of Gynecology, Herning Hospital, between September 2016 to end of December 2017. Sample size is estimated based on recommendations from the literature (8)(Cala V. et al. 2012). The study consists of two sub-studies (A and B). Each of the two sub-studies includes 40 procedures performed by two experienced laparoscopists with 20 procedures each.

A: Determination of learning curve for two similar experienced surgeons, for 40 robotic *multiport* hysterectomies – 20 hysterectomies per surgeon.

Inclusion criteria for the learning curve studies are hysterectomy on benign indication, ASA group 1 or 2, BMI (body mass in kg/heights in metres²) less than 35 kg/m² (for R-SS hysterectomy less than 30), uterine size less than 300 g estimated by ultrasound, using Ferraris formula.

Exclusion criteria are risk of adhesions, prior extensive abdominal surgery and prior midline incision, cutis laxa of abdomen surgery, endometriosis, and more than 1 cesarean section.

The procedure is video recorded and peri-and postoperative data are collected prospectively. Various steps during the procedure are determined such as various split time measurements like docking time, console time, vaginal cuff suturing, incision start, skin-to-skin and closure time. Uterine size and blood loss, as well as patient demographic data are registered.

B. The on-going study estimates the learning curve for *R-SS* hysterectomy. In- and exclusion criteria as for Study 1 except for inclusion criteria of BMI less than 30 kg/m²

C. Further, a retrospective cohort from the first robotic hysterectomies in 2014 until recently will be evaluated. The surgeries in the prospective studies are performed using the Da Vinci Xi surgical system and in the retrospective study using the Da Vinci Si Multiport system. Due to its design only crude incidences on perioperative variables will be evaluated.

Study 2

Robotic single-site hysterectomy compared to laparoscopic multiport hysterectomy – a prospective randomized controlled study; cosmetic satisfaction and surgical outcome.

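### Study 1 names uterine size as an influence to be understood and records it, but no planned analysis uses it, so the non-randomised learning curves cannot separate learning from case difficulty

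*Protocol*

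**What the plan says.** The Background, on learning curves, states that "proper knowledge is important to which extent e.g. BMI, uterine size, and docking time at the robotic console influence the procedure" and links this to choosing suitable patients for each surgical option. The Aim of study lists the learning curve, the duration of operation with its steps, and blood loss as secondary outcomes.

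Study 1 compares robotic single-site with robotic multiport hysterectomy. Each technique has 40 procedures, 20 by each of two surgeons, and no randomisation is described. Entry requires "uterine size less than 300 g estimated by ultrasound, using Ferraris formula", and the text adds: "Uterine size and blood loss, as well as patient demographic data are registered". The retrospective cohort is restricted to crude incidences. Study 2 randomises 62 v 62 women and takes over the entry criteria: "Eligibility criteria are the same as for study 2B" (apparently meaning 1B, since no 2B is described).

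The Statistics section gives two covariate lists:
- For repeated measurements analysed by two-way ANOVA: "potential confounding variables like age, BMI, surgeon, and additional surgery added".
- For the logistic model: "the various split times, surgeon, age, BMI, parity, as independent variables". Its outcome is the type of operation: "Logistics regression analysis was performed with surgical procedure as dependent variable".

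Learning curves are to be drawn for each surgeon, for each procedure and combined. No covariate is named for them.

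**The concern.** The protocol poses a question about uterine size, collects the data to answer it, and then plans no analysis that could. BMI, named beside uterine size in the Background, is in both covariate lists.

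The consequence lies in Study 1. A learning curve is a trend of time on case number. If uteri become larger over a surgeon's series, for instance because easier cases were taken first, real learning is partly masked. If they become smaller, learning is exaggerated. Likewise, if single-site and multiport cases differ in uterine size, the difference passes into the comparison of operating times. Without uterine size in the model, the reader cannot tell which of these has happened.

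**Working it through.** **The plan's own figure.** The protocol gives no calculation on this point. Its only computed figure is the Study 2 sample size, which reproduces: n = 2 × (1.96 + 0.84)² × (8/4)² ≈ 62.8, so 63 per group against 62 stated (power 79.5% at 62). It plays no part below.

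**The passages side by side.**

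| Variable | Named in Background as an influence | ANOVA list | Logistic list | Variables whose distribution is described | Learning curves |
|---|---|---|---|---|---|
| BMI | yes | yes | yes | yes | no |
| Docking time | yes | no | among the split times | among the split times | not stated |
| Uterine size | yes | no | no | no | no |

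**Bias in a learning curve.** If time rises by b min per gram and mean uterine weight drifts by D grams from first to last case, the unadjusted curve misstates the gain by b × D. The documents give neither b nor D, so both are assumptions.

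| Drift D | b = 0.10 min/g | b = 0.15 min/g | b = 0.20 min/g |
|---|---|---|---|
| 0 g | 0 min | 0 min | 0 min |
| 50 g | 5 min | 7.5 min | 10 min |
| 100 g | 10 min | 15 min | 20 min |

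Upward drift hides this much learning; downward drift adds as much false learning.

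**Illustration by simulation.** Assumed: 20 cases, true gain 1.5 min per case × 19 steps = 28.5 min, b = 0.15 min/g, weight SD 50 g around the trend, residual SD 20 min. Linear regression of time on case number, without and with weight; 10,000 series per entry.

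| Drift over the series | Unadjusted gain | Adjusted gain | Chance of a significant gain, unadjusted v adjusted |
|---|---|---|---|
| 100 g down | 43.5 min | 28.5 min | 75% v 33% |
| 50 g down | 35.9 min | 28.4 min | 59% v 40% |
| none | 28.6 min | 28.7 min | 41% v 43% |
| 50 g up | 20.9 min | 28.7 min | 24% v 40% |
| 100 g up | 13.8 min | 28.2 min | 13% v 32% |

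The adjusted gain stays near the truth throughout. With no drift, adjustment costs nothing on average. The high unadjusted chance under downward drift comes from the bias and is not real power.

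**Technique comparison in Study 1, 40 v 40.** In SD units the bias is ρ × imbalance, where ρ is the correlation of uterine size with operating time. For assumed ρ of 0.1, 0.3 and 0.5, an imbalance of 0.5 SD shifts operating time by 0.05, 0.15 and 0.25 SD. Chance alone gives the imbalance a standard error of √(2/40) = 0.22 SD; selection can add to that.

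**Study 2, 62 v 62.** The expected imbalance is zero, with standard error √(2/62) = 0.18 SD. Adjustment gives an effective group size of 62/(1 − ρ²), about 63, 68 and 83 for the same values of ρ. That is precision, not removal of bias.

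**The case against.** The case against has several sound parts.

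- The ANOVA list is introduced by *like*, so it gives examples and does not exclude uterine size. It also concerns repeated measurements, whereas skin-to-skin time and blood loss occur once per woman. A statistical analysis plan that is not shown could add the covariate. This stands, and the absence of a word from that list would be a weak point on its own. What remains is that the protocol raises the question itself, chooses covariates, and describes learning curves with no case-mix term.
- A reader might infer that adding uterine size to the logistic model would repair matters. It would not: procedure is the outcome there and split times are predictors, so operating time would not be adjusted.
- A reader might infer that the Study 2 operating-time comparison is confounded by case difficulty. Randomisation rules out systematic confounding.
- A reader might infer that uterine size is recorded for every woman in the programme. The text says so for prospective Study 1 and implies an ultrasound estimate for Study 2 through eligibility. It does not say so for the retrospective cohort.
- No passage says that small uteri were taken first, and the 300 g limit narrows the range. Both are true. The limit reduces variation without removing it, and the direction of any drift is unknown.
- Learning curve, operating time and blood loss are secondary outcomes. The primary outcomes and the sample size are untouched.

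**Conclusion.** The point holds for prospective Study 1. As written, the plan has no analysis that answers its own question about uterine size, and none that separates learning or technique from case difficulty in non-randomised series of 20.

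The size is unknown from the documents. Under the assumed slopes and drifts it runs from 0 to 20 min in either direction. A reader might take from the 100 g upward example that half of the learning gain is hidden (15 of 28.5 min). That is the largest drift considered combined with invented inputs; with no drift there is no bias, and the documents do not show which case applies.

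For Study 2 the covariate is an optional precision gain for operating time and blood loss, of a size that depends on an unknown correlation. The retrospective cohort, limited to crude incidences, is not affected. This is an inexpensive improvement to a listed secondary outcome and does not threaten the trial's main comparison.

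**What to change.** In the Statistics section, for Study 1:

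1. Fit learning-curve models with operating time or a split time as the outcome, on case number and uterine weight (continuous), by surgeon and technique.
2. Include the same covariate in the comparison of single-site with multiport robotic cases.
3. Use the preoperative ultrasound estimate already required for eligibility, and say so, because the text does not state which measure of uterine size is registered.
4. Report the uterine-weight coefficient with its confidence interval. This answers the Background question.

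Do not rely on the logistic model with procedure as outcome for this purpose. In Study 2 the covariate may be named as optional for operating time and blood loss.

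The cost is wording and one degree of freedom per model. In a 20-case linear fit the residual degrees of freedom fall from 18 to 17, which matters a little. If weight does drift with case number, the adjusted slope is also less precise, which is the price of removing the bias. No new data are needed.
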